G. Exploratory Research Hypotheses

1. Blood periostin (or other biomarkers such as blood eosinophils, or eNO) will be as effective as sputum eosinophils at identifying patients likely to respond to ICS.

2. The Asthma Index, together with associated questionnaires, will characterize the time course and magnitude of morbidity associated with asthma exacerbations and serve as a tool for studying interventions for management of asthma exacerbations.

3. Among asthmatic participants who are persistently non-eosinophilic, the preference for ICS is not greater than for LMA.

4. Among asthmatic participants with sputum eosinophilia, the preference for ICS is greater than for LMA.

H. Primary Outcome Measure

The primary outcome is a hierarchical composite of three measures of asthma control, assessed during the last 8 weeks of each 12 week treatment

period: Treatment Failure (TF), Asthma Control Days (ACD), FEV₁.

The definition of **TF** comes from the Symptom-Based Action Plan that was utilized successfully in the ACRN IMPACT Study ³ and includes:

- Awakening from asthma three or more times in a two-week period or on two consecutive nights, or
- Using albuterol for relief of symptoms four or more times/day for two or more consecutive days, or
- Albuterol has been relieving symptoms for less than four hours after each treatment over a 12-hour period, or
- Using albuterol for relief of symptoms daily for seven days, and this use exceeds two times the weekly use of albuterol in the baseline period, or
- exercise induces unusual breathlessness.

ACDs will be documented in daily diaries, and are defined as: A day with no rescue albuterol use (pre-exercise albuterol will not be counted), no non-study asthma medications, no daytime asthma symptoms (shortness of breath, wheezing, chest tightness, phlegm/mucus rated as mild, moderate or severe, or cough rated as moderate or severe), no nighttime asthma symptoms, no unscheduled healthcare visits for asthma, and no PEF < 80% of predetermined baseline.

FEV₁ is a standard outcome measure for asthma, and was used in a similar hierarchical preference analysis in BADGER¹⁸.

I. Secondary Outcome Measures

Each of the three components of the composite outcome (TF, ACD, FEV₁) will be analyzed separately as secondary outcomes. Other secondary outcomes include PEF, asthma exacerbations, time to treatment failure and time to first exacerbation.

J. Exploratory Outcome Measures

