An important exploratory question is whether other biomarkers such as blood periostin, blood eosinophils or eNO can be used instead of sputum eosinophils to identify patients with differential treatment preferences to ICS and LMA. Although recent data suggest that airway eosinophilia, elevated FeNO, and serum periostin may all be markers of TH₂ inflammation, we have chosen to stratify our populations based on sputum eosinophilia, a robust biomarker that has been well-characterized. Periostin, a 90 kD protein produced by airway epithelium in response to IL-13, is an alternate candidate biomarker, but more information is needed about how blood periostin levels relate to airway eosinophil levels, and about the threshold value for defining abnormal periostin levels. FeNO is another candidate biomarker of airway eosinophilia and ICS responsiveness but two recent reports have questioned its utility as a biomarker of airway eosinophilia ^{1, 19}. In this prospective study we propose to collect serum for periostin and measure eNO and blood eosinophils so that we can evaluate the relative utility of these three simpler tests as biomarkers of airway eosinophilia and ICS treatment response in mild moderate asthma. We also propose to assess the bronchodilator response (BR) to both beta agonist and

[figure not shown]
anticholinergic agents to determine whether the eosinophil-negative group has different bronchodilator responses to albuterol vs. ipratropium (Atrovent® HFA). We will include adolescents 12-18 years old in this study because asthma guidelines combine this group with adults, but the study will not be powered for the comparison between adults and adolescents. This important exploratory analysis will provide clues as to the prevalence of eosinophil negative asthma in adolescents, the utility of and appropriate cut point for periostin, and the similarity or difference in the treatment response between adolescents and adults.

Additional exploratory outcomes include a number of tools and endpoints to characterize the time course of asthma exacerbations. The Protocol Review Committee previously suggested that AsthmaNet trials be used to gather preliminary information on exacerbations, as was also suggested in a recent NIH Outcomes Workshop ²⁰. These assessments will be incorporated within the main SIENA protocol and visit structure, to minimize both participant and site burden, and to enhance safety follow-up.

IV. PROTOCOL OVERVIEW

A. Protocol Design

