4. Application of univariable and multivariable logistic regression that uses sputum eosinophils, blood eosinophils, FENO and serum periostin, as well as bronchodilator reversibility, measures of atopy, and other phenotypic characteristics from both eosinophilic and non-eosinophilic participants to construct ROC curves and c (concordance) statistics to identify “cutpoints” for each biomarker (which also can be compared with previously suggested cutpoints) to examine the value of these biomarkers as predictors of response to treatments.

All of the analyses described above will follow the intention-to-treat paradigm whereby all available data from randomized participants are included in the analyses regardless of information about deviations from study protocol.

D. Statistical Analysis Plan for Additional Secondary Outcomes

We will analyze separately each of three components of the composite outcome as secondary outcomes. We will apply a proportional hazards regression analysis for the time to treatment failure, with a random effect term (frailty) for the SIENA participant to account for the correlations within the SIENA participant ²⁷. The proportional hazards regression model will include fixed terms for treatment regimen, sequence, period, and season of enrollment and an additional random effect term for clinical site. We will apply a linear mixed-effects model for longitudinal data on ACDs and FEV₁. The statistical model will include

(1) fixed effects for treatment regimen, sequence, period, and season of enrollment (spring, summer, fall, winter) nested within each of the eosinophilic and non-eosinophilic phenotypes. (2) a random effect for clinical site within each of the eosinophilic and non-eosinophilic phenotypes, and (3) a 7×7 unstructured variance-covariance matrix for the seven measurements per participant (baseline and two timepoints within each of the three periods). We will apply a similar statistical approach for the other secondary outcomes that are measured on a continuum, such as diary peak flow values and logarithmic-transformed methacholine challenge PC_{20} . We will analyze time to asthma exacerbation in a manner similar to that for time to treatment failure.

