We will pursue additional secondary analyses to investigate whether baseline measurements of the biomarkers (blood eosinophils, periostin, and exhaled nitric oxide) significantly predict any of these secondary outcomes. We will achieve this by including the biomarkers in the statistical models described in the previous paragraph.

Finally, we will perform exploratory subgroup analyses of the primary and secondary outcomes within levels of gender, minority status, age group, baseline BMI, and baseline FEV_1 .

E. Missing Data

Because of the possibility of drop-outs and other missed visits, there will be some missing data. The statistical models and analyses that are planned for the

primary and secondary outcomes assume that the data are missing-at-random (MAR). Because we are applying likelihood-based methods for the data adjustment with primary outcome and for all of the secondary outcomes, MAR data still yield valid estimates. Although not expected, if it appears that the MAR assumption is not reasonable, then we will invoke shared parameter models to simultaneously model the time to drop-out and the individual secondary outcome²⁸.

F. Interim Analyses

There will be no formal interim analysis of efficacy in this trial. Nevertheless, interim statistical analyses to evaluate the safety of the three treatment regimens will be presented to the AsthmaNet Data and Safety Monitoring Board (DSMB) semi-annually for review. Based on the results of these interim analyses, the DSMB will recommend to the NHLBI the continuation or discontinuation of the trial. In addition, the DSMB will be monitoring all of the safety data throughout the course of the trial and will be notified within 72 hours of any serious adverse event (SAE) that is deemed both unexpected and related to the study. All SAEs will be reviewed at each 6-month review.

G. Power Calculations

The target sample for the SIENA trial is 336 randomized participants, 74 in the eosinophilic phenotype and 262 in the non-eosinophilic phenotype, because we anticipate a 1-to-3.5 ratio, or smaller, of the eosinophilic phenotype to the non-eosinophilic phenotype.

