For the co-primary comparisons within the non-eosinophilic phenotype, the sample size of 262 yields statistical power of 0.9 with two-sided, 0.025 significance level tests (Bonferroni correction), while allowing for a 15% drop-out rate, to detect $p_{Eos-,ICS>Placebo} - p_{Eos-,Placebo>ICS} = 0.20$ (and to detect $p_{Eos-,LMA>Placebo} - p_{Eos-,Placebo>LMA} = 0.20$). We assume that 30% of the participants will not display a preference for ICS versus placebo and therefore not included in the primary analysis (and that 30% of the participants will not display a preference for LMA versus placebo). The following table illustrates the level of statistical power for selected sample sizes.

N	$p_{Eos-,ICS \approx Placebo}$ or $p_{Eos-,LMA \approx Placebo}$	$p_{Eos-,ICS>Placebo} - p_{Eos-,LMA>Placebo}$ or $p_{Eos-,Placebo>ICS} - p_{Eos-,Placebo>LMA}$	Statistical Power
	0.30	0.20	
202	0.30	0.20	80%
228	0.30	0.20	85%
262	0.30	0.20	90%

With respect to the secondary analysis of the primary outcome, the following table illustrates the statistical power for detecting $p_{Eos+,ICS>Placebo} = 0.71$ and $p_{Eos-,ICS>Placebo} = 0.45$, yielding a difference of 0.26 between the two phenotypes (and for detecting $p_{Eos+,LMA>Placebo} = 0.71$ and $p_{Eos-,LMA>Placebo} = 0.45$, yielding a difference of 0.26 between the two phenotypes).

EOS-Negatives		EOS-Positives			Statistical Power
N	$p_{Eos-,ICS>Placebo}$ or $p_{Eos-,LMA>Placebo}$	N	$p_{Eos+,ICS>Placebo}$ or $p_{Eos+,LMA>Placebo}$		
202	0.45	58	0.71		80%
228	0.45	66	0.71		85%
262	0.45	74	0.71		90%

For the secondary analysis of comparing the ICS and LMA treatments within the non-eosinophilic phenotype, there is 90% statistical power with a sample size of 262 to detect a difference of 0.185 ($= p_{Eos-,LMA>ICS} - p_{Eos-,ICS>LMA}$) with a two-sided, 0.05 significance level test.

H. Anticipated Results

Our primary hypothesis is that the response to ICS and LMA will be different in participants with and without airway eosinophilia. We anticipate that ICS will be more effective in asthmatics with airway eosinophilia and that LMA will be more effective in asthmatics who are persistently non-eosinophilic.

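### Section VIII.C, secondary analysis 4: biomarker cutpoints and c statistics are derived and judged on the same participants without internal validation, so multivariable c statistics and accuracy at derived cutpoints will be biased upward

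*Combined protocol and SAP*

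**What the plan says.** Section VIII.C, secondary analysis 4, specifies logistic models with one predictor and with several. The analysis "uses sputum eosinophils, blood eosinophils, FENO and serum periostin, as well as bronchodilator reversibility, measures of atopy, and other phenotypic characteristics" as predictors, taken "from both eosinophilic and non-eosinophilic participants". The models serve "to construct ROC curves and c (concordance) statistics to identify" a cutpoint for each biomarker. The same sentence gives the one outside reference and the purpose: "which also can be compared with previously suggested cutpoints) to examine the value of these biomarkers as predictors of response to treatments".

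The item does not define response, say how ties are handled, or close the list of predictors. No split sample, cross-validation, bootstrap, shrinkage or external validation appears in the documents, and nothing allows for the cutpoint search.

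Section III.G, hypothesis 1, says that periostin or another of the simpler markers "will be as effective as sputum eosinophils at identifying patients likely to respond to ICS". Section III.J introduces the topic with "An important exploratory question is whether other biomarkers such as blood periostin, blood eosinophils or eNO can be used instead of sputum eosinophils". Section III thus labels the question exploratory, while section VIII.C lists the analysis among the secondary analyses.

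**The concern.** A model fitted to a set of participants separates those participants better than it separates new ones. The gap grows with the number of predictors and shrinks with the number of participants. Likewise, a cutpoint picked because it performs best on a data set will look better there than elsewhere. Here the number of predictors is open-ended, the sample is modest, and no step measures or removes the gap.

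What is at stake is the claim that a simpler test could stand in for sputum induction. Sputum eosinophils already have a pre-set 2% cutpoint (section IV.G). If that is kept while the other markers get cutpoints tuned on trial data, a comparison of accuracy at the cutpoints favours the tuned markers. Periostin is the most exposed, because section III.J says its threshold still needs more information.

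**Working it through.** **Inputs from the documents (section VIII.G).** The target is "336 randomized participants, 74 in the eosinophilic phenotype and 262 in the non-eosinophilic phenotype". The co-primary comparisons use "two-sided, 0.025 significance level tests (Bonferroni correction), while allowing for a 15% drop-out rate", 30% of participants with no preference, and a difference of 0.20 between the two preference probabilities. Planning values for superiority over placebo are 0.71 (eosinophilic) and 0.45 (non-eosinophilic).

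**Step 1: reproduce the plan's own figure.** The documents give no figure for the biomarker analysis, so the stated power serves only to anchor the sample size. With 30% ties and a difference of 0.20, the two probabilities are 0.45 and 0.25. Among the non-tied, the win probability is 0.45 / 0.70 = 0.643. The expected number of non-tied participants is 262 × 0.85 × 0.70 ≈ 156. A two-sided exact binomial test at 0.025 then has power 0.903 (0.902 averaged over the random number of ties), against 0.90 stated. Averaged in the same way, N = 202 gives 0.801 and N = 228 gives 0.853, against 0.80 and 0.85. The plan's figures reproduce.

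**Step 2: sample size for secondary analysis 4.** The plan leaves tie handling open for this item, so two cases are taken.
- Ties dropped: 336 × 0.85 × 0.70 ≈ 200, with response proportion 0.64.
- Ties kept as non-response: 336 × 0.85 ≈ 286, with response proportion rounded to 0.50. The weighted planning value is (74 × 0.71 + 262 × 0.45) / 336 = 0.507.

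The 15% and 30% are stated for the non-eosinophilic comparison. Applying them to all 336 is an assumption.

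**Step 3: apparent performance of useless markers.** Predictors were simulated as independent standard normal noise, unrelated to response, with 1,500 simulated trials per setting. The number of predictors, k, is an assumption. In new participants, the same models gave a mean c of 0.50 throughout.

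| k | Mean apparent multivariable c, n = 200 | Trials with c ≥ 0.60 | Mean apparent multivariable c, n = 286 | Trials with c ≥ 0.60 |
|---|---|---|---|---|
| 4 | 0.58 | 23% | 0.56 | 7% |
| 7 | 0.61 | 57% | 0.59 | 27% |
| 10 | 0.63 | 85% | 0.60 | 54% |
| 15 | 0.66 | 98% | 0.63 | 88% |

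A c of 0.70 or more occurred in 10.5% of trials at n = 200 and k = 15, and in about 1% or fewer in every other setting.

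**Step 4: one noise marker.**
- Univariable c, direction left free: mean 0.53. It reached 0.60 in about 2% of trials (n = 200) or 0.3% (n = 286).
- Best of k markers taken singly: mean c 0.56 to 0.59 (n = 200) or 0.55 to 0.57 (n = 286) for k = 4 to 15. Correlated markers would lower these values.
- Youden index (sensitivity + specificity − 1) at the best cutpoint: 0.12 (n = 200) or 0.10 (n = 286) apparent, and 0.00 in new participants.
- If an unadjusted chi-square test were run at that cutpoint, p < 0.05 would occur in about 40% of trials instead of 5%, or about 24% if the marker's direction were fixed in advance. The plan specifies no such test, so this only illustrates the effect of the search.

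**Step 5: what correction achieves.** Corrected value = apparent value − mean over resamples of (performance of the refitted rule in the resample − its performance in the original data). This used 100 resamples in each of 150 simulated trials per setting. Mean multivariable c for noise fell from 0.58–0.66 to 0.53–0.55 (n = 200) and from 0.56–0.63 to 0.52–0.54 (n = 286). The one-marker Youden index fell from 0.10–0.13 to 0.02–0.05. As an example at n = 200 and k = 15, the excess over 0.50 fell from 0.162 to 0.052, so about two thirds was removed. Across settings the share removed was roughly two thirds to three quarters.

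**The case against.** A reader might infer that worthless markers will generally look predictive and that the analysis would endorse one. The documents do not support that. Replacing sputum with one simpler test is largely a marker-by-marker question, and the univariable c of a pre-named marker uses no cutpoint and is barely inflated. The plan sets no c threshold, no decision rule and no test at a chosen cutpoint. The hypothesis in section III.G is comparative, and sputum eosinophils enter the same models, so optimism in a single marker's univariable c affects both sides alike. Section III labels the question exploratory, and comparison with previously suggested cutpoints is a genuine safeguard because those were not chosen on these data. The documents are silent on correction but do not exclude it.

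All of this stands, and it limits the point to two quantities: the multivariable c and accuracy at derived cutpoints. It does not remove the bias in either. The comparison with earlier cutpoints is worded as optional, nothing says which result governs if the two disagree, and it helps least for periostin. Nor does the shared-optimism argument cover a fixed 2% sputum cutpoint set against tuned cutpoints for the other markers.

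**Conclusion.** The point holds in a limited form. Followed as written, secondary analysis 4 yields multivariable c statistics and derived-cutpoint accuracy that are biased upward. For noise predictors the excess in mean c is 0.08 to 0.16 with ties dropped and 0.06 to 0.13 with ties kept, over k = 4 to 15. The excess in the one-marker Youden index is about 0.12 or 0.10. The excess in a single pre-named marker's univariable c is about 0.03, which is of little consequence.

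These sizes rest on assumed predictor counts, independent normal markers, and the two tie conventions. No figure in the plan is wrong, and the co-primary analyses are untouched. The matter is a minor improvement to an analysis whose question section III calls exploratory.

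**What to change.** Amend secondary analysis 4 in section VIII.C as follows.
- List the candidate predictors, and define response and the handling of ties for this item.
- Report bootstrap optimism-corrected c statistics and cutpoint accuracy beside the apparent values. Repeat the cutpoint search, and any variable selection, inside each resample.
- Give bootstrap intervals for the derived cutpoints.
- Make previously suggested cutpoints, where they exist, the main assessment of each marker.
- Label trial-derived cutpoints, notably any for periostin, as hypothesis-generating.

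The cost is a few sentences in the SAP and slightly more computing, with no new data or visits. The reported c statistics will be lower. Because the correction leaves roughly a quarter to a third of the optimism in place, a corrected c slightly above 0.50 should still not be read as evidence of value.

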The AsthmaNet Steering Committee will monitor SIENA recruitment and continually reevaluate the likelihood of completing recruitment by May 2016. Depending on the results of this evaluation, the Steering Committee may recommend to the DSMB that a switch to MDI should be made. If a switch is made, all participants will complete the study using whichever formulation they receive at randomization. No participants will switch from DPI to MDI during the course of the study. The randomization plan and the statistical analysis plan will be modified accordingly. In particular, we will insert an additional level of stratification for randomization according to DPI/MDI assignment. The current statistical plan is to include the stratifying variables as blocking factors, so DPI/MDI assignment will be included as a blocking factor in the statistical

analysis.

Update November 2015: Due to lagging recruitment and mometasone DPI expiration issues, a switch to mometasone MDI is necessary. *Merck* has provided mometasone and mometasone placebo in the form of Asmanex® HFA, 200 mcg/puff. Participants will take 1 puff twice daily (total dose active drug = 400 mcg). *Merck* will coordinate the blinding of drug with information provided by the DCC. A third-party packager will label with additional regulatory information.

Contingent Statistical Analysis

Because SIENA invokes a three-way crossover design, a stratified randomization based on prognostic factors is not critical. Instead, we only will invoke clinical site within phenotype (eosinophilic, non-eosinophilic) as a stratifying variable with permuted blocks of size six (one complete cycle of the six). As indicated above, if a DPI/MDI switch occurs, then we will include this as another stratification variable. In particular, the stratification will be according to DPI/MDI status nested within clinical center, which is nested within phenotype.

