The statistical analysis plan for the primary and secondary outcomes is described in Section VIII.C. With respect to the primary outcome variable, we will apply a linear mixed-effect model that includes (1) fixed effects for treatment regimen, sequence, period, and season of enrollment (spring, summer, fall, winter) nested within each of the eosinophilic and non-eosinophilic phenotypes, (2) random effects for clinical site within each of the eosinophilic and non-eosinophilic phenotypes, and (3) a 7×7 unstructured variance-covariance matrix for the seven measurements per participant within each of the eosinophilic and non-eosinophilic phenotypes. We will account for the additional stratifying variable of DPI/MDI status by including it as another fixed-effect variable in linear mixed-effects model.

Obviously, completion of the entire study with the same manufacturer's lot of active drug and placebo is ideal. However, if *Merck* is not able to provide us with sufficient placebo DPI, we do not believe that the switch from active DPI to active MDI will negatively impact the scientific validity of the study.

The goal of the study is to examine whether subjects with *mild-to-moderate asthma* who are persistently non-eosinophilic require a different treatment strategy than those with sputum eosinophilia. Preliminary data suggest that subjects without sputum eosinophilia (presumed "TH2-low" asthma) do not respond to inhaled corticosteroids or to prednisone. In SIENA we will enroll subjects with persistent asthma who meet the EPR-3 criteria for *Mild-to-Moderate Asthma* and for whom *Step 2 Treatment* (Preferred = Low-dose ICS) is recommended. However, because we believe that ~50% of these subjects will not respond to ICS, we will provide *Step 3 Treatment* (Medium-dose ICS), to ensure that the issue is not too little ICS. In the case of Mometasone, EPR-3

defines "low-dose" as 200 mcg/day and "medium dose" as 400 mcg/day. Because Merck will be fulfilling FDA criteria for equivalence, we anticipate that the doses delivered will be comparable, but even if there is a small difference in dose delivered between the DPI and MDI preparations, that dose should be sufficiently high on the flat portion of the dose-response curve that it will not impact the outcome.

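### The time-to-treatment-failure and time-to-exacerbation models have no phenotype term, so each treatment contrast is one pooled hazard ratio; and the seasonal check uses enrollment season, which misses a seasonal effect on asthma control

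*Combined protocol and SAP*

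**What the plan says.** Section III.I makes both time-to-event endpoints secondary outcomes: "Other secondary outcomes include PEF, asthma exacerbations, time to treatment failure and time to first exacerbation".

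Section VIII.D gives the model for time to TF: "The proportional hazards regression model will include fixed terms for treatment regimen, sequence, period, and season of enrollment", with random terms for participant and clinical site. It then adds: "We will analyze time to asthma exacerbation in a manner similar to that for time to treatment failure". The linear mixed model for asthma control days and FEV1, in the same paragraph, has the same four fixed effects but places them "nested within each of the eosinophilic and non-eosinophilic phenotypes", and nests the site effect as well.

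Section VIII.C describes a logistic sensitivity analysis of the composite preference among participants without a tie. Its declared purpose is to look at period and seasonal effects. The covariates are period differences, season of enrollment and ICS device (DPI or MDI), with no interaction.

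**The concern.** **Phenotype.** Phenotype is a randomization stratum, and Section VIII.H says: "Our primary hypothesis is that the response to ICS and LMA will be different in participants with and without airway eosinophilia". A hazard model without phenotype and its interaction with treatment can show neither the effect in each phenotype nor whether the effects differ. A pooled ratio can suggest benefit in a group that has none and understate it in the group that has it.

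**Season.** The outcome of the logistic check is a within-person comparison of two periods. Season of enrollment is one value per person. A seasonal effect on asthma control acts through the difference between the seasons of the two periods, and its sign depends on which treatment came first. If the covariate cannot register that, a null result says little about season, which is what the check is for.

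**Working it through.** **Does another part of the plan supply phenotype?**

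- Appendix D says: "The current statistical plan is to include the stratifying variables as blocking factors". Phenotype is a stratifying variable, so this adds at most a main effect and leaves one treatment hazard ratio.
- The nesting in Appendix D, Contingent Statistical Analysis, belongs to a different model and outcome: with respect to the primary outcome, "we will apply a linear mixed-effect model that includes (1) fixed effects for treatment regimen".
- Section VIII.D adds blood eosinophils, periostin and exhaled nitric oxide to its models, but not sputum phenotype. It also plans "exploratory subgroup analyses of the primary and secondary outcomes within levels of gender, minority status, age group, baseline BMI" and baseline FEV1. Phenotype is not on that list.

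**Size of the pooling.** The plan gives 262 and 74 participants (VIII.G) but no event rates or hazard ratios. Assume ICS hazard ratios of 1.0 (non-eosinophilic) and 0.4 (eosinophilic), and let k be the ratio of eosinophilic to non-eosinophilic base rates. With few events,

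pooled HR ≈ (262 + 74k × 0.4) / (262 + 74k).

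Simulations used six balanced sequences, three 8-week windows, exponential times and non-eosinophilic placebo TF of 8, 15 or 30% (assumed). Cox models were fitted to data without frailty and with gamma frailty of variance 1 (500 trials per setting). A constant-baseline model with normal participant frailty was fitted to data with log-normal frailty, sd 1 (150 trials per setting). The site effect was omitted. Ranges span all settings, except that the main-effect column is Cox fits only. Tests are two-sided at 0.05.

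| k | Formula | Simulated pooled HR | With phenotype main effect | Pooled test significant |
|---|---|---|---|---|
| 0.5 | 276.8/299 = 0.93 | 0.88–0.94 | 0.90–0.94 | 4–9% |
| 1 | 291.6/336 = 0.87 | 0.83–0.89 | 0.85–0.88 | 6–21% |
| 2 | 321.2/410 = 0.78 | 0.76–0.83 | 0.78–0.82 | 12–36% |
| 3 | 350.8/484 = 0.72 | 0.73–0.81 | 0.72–0.79 | 18–48% |

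In this scenario 262/336 = 78% have no ICS effect. A model with the interaction recovers about 1.0 and 0.33–0.47.

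**Season: the plan's own figures first.** With 30% ties and a difference of 0.20 (VIII.G), the two preference probabilities are 0.45 and 0.25, so the preference among non-ties is 0.45/0.70 = 0.643. Non-ties number 262 × 0.85 × 0.70 = 155.9. Exact two-sided binomial power at 0.025, averaged over the number of non-ties, is 80.1%, 85.3% and 90.2% for N = 202, 228 and 262, which matches the plan's 80, 85 and 90%.

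**Schedule.** Counted from randomization, the analysis windows are weeks 4–12, 16–24 and 28–36, with midpoints 8, 20 and 32. A season is 365.25/7/4 = 13.04 weeks. Adjacent periods have midpoints in different seasons in 12/13.04 = 92% of cases, and periods 1 and 3 always do. Over all orders this is (2 × 92 + 100)/3 = 95%. Enrollment season equals the season of the period 1 midpoint in 0% of cases (counted from Week 0, 6-week run-in), 8% (4-week run-in) or 39% (counted from randomization). It never equals that of period 2 or 3.

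**Why the covariate misses it.** Let s be the seasonal effect on control. The preference logit shifts by s(ICS period) − s(placebo period). Swapping the order reverses the sign, and both orders are equally likely within each enrollment season. The main effect of enrollment season therefore averages it out.

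**Simulation.** 156 non-ties, marginal preference held at 0.643, one season different, uniform enrollment, 2,000 trials per setting, 5% likelihood-ratio tests with 3 df.

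| Scenario | Size (logits) | Enrollment season | Season-of-period differences |
|---|---|---|---|
| No seasonal effect | 0 | 5% | 6% |
| Season affects control | 0.5 | 5% | 35% |
| | 1 | 5% | 92% |
| | 2 | 9% | 100% |
| Treatment benefit varies by season | 0.5 | 7% | 13% |
| | 1 | 9% | 32% |
| | 2 | 20% | 77% |

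When the benefit itself varies by season, enrollment season has some power, but much less.

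**The case against.** **Phenotype.** The plan never says the phenotypes are pooled. It introduces these models as analyses of the components of a composite that VIII.C does analyze by phenotype, so nesting may have been intended. That is possible, but the terms are listed explicitly and the neighboring model states its nesting. If nesting was meant, one sentence settles it.

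The phenotype question itself is answered elsewhere, because VIII.C tests the composite within and between phenotypes and TF is its first tier. This stands: the loss is confined to two secondary analyses.

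The assumed pair 1.0 and 0.4 is one scenario. A ratio of 1.0 conflicts with the co-primary hypothesis that ICS beats placebo in the non-eosinophilic group, although Sections V.A and IX.B say this group is not expected to respond. With 0.8 and 0.5, the pooled value is (209.6 + 37)/336 = 0.73 at k = 1 and (209.6 + 74)/410 = 0.69 at k = 2, nearer the non-eosinophilic value. The size of the distortion thus depends on assumption. That the pooled model cannot separate the phenotypes does not. Nor are the significant pooled tests false positives, since 22% do have an effect in the scenario.

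**Season.** The seasonal effect sizes are assumed, and VIII.C specifies no test of the season term, only adjustment. But adjusting for a covariate that averages the effect out does not adjust for it either, and assessing season is the declared aim.

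An enrollment-season-by-period interaction would be a smaller change. In a separate simulation (1,000 trials, seasonal pattern +a, 0, −a, 0) it detected the effect in 75% of trials at a = 0.5 and 100% at a = 1.0, against 83% and 100% for season-of-period differences. It is a workable alternative, but it uses 6 df. With uneven enrollment (40/30/20/10%) and no effect it rejected in 9.7% of trials, against 5.3%.

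**Conclusion.** Both parts hold. That the hazard models list no phenotype term, and that the seasonal covariate is constant within a participant, can be read directly from the text.

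As written, the time-to-TF and time-to-exacerbation analyses cannot give phenotype-specific effects or test whether they differ, and a phenotype main effect alone would hardly change this. The pooled values rest on the assumed hazard ratios, event rates and k. The composite, asthma control days and FEV1 analyses are unaffected.

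The seasonal check has essentially no power against a seasonal effect on control of up to 1 logit (5%), and little against seasonal variation in benefit. The exact co-primary tests remain valid because sequences are randomized, so only the check fails. The change should be made; the phenotype part matters more.

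**What to change.** **Hazard models (VIII.D).** Add phenotype and treatment-by-phenotype to both models, or fit them by phenotype. Report phenotype-specific hazard ratios with intervals and the interaction test. Allow descriptive reporting where eosinophilic events are too few, for example none in one of the compared arms.

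Precision in the eosinophilic group will be limited. On the assumptions above:

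| k | 95% interval: estimate multiplied and divided by | Interaction power |
|---|---|---|
| 0.5 | 2.9–11 | 1–39% |
| 1 | 2.1–5.2 | 8–61% |
| 2 | 1.8–3.2 | 24–82% |
| 3 | 1.6–2.6 | 30–91% |

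At 8% non-eosinophilic placebo TF, an eosinophilic ICS or placebo arm has no event in 30–32% of trials at k = 0.5 and 6–10% at k = 1. Exacerbations are likely to be rarer still. This argues for showing the uncertainty, not for pooling.

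**Seasonal check (VIII.C).** Replace season of enrollment with the difference in calendar-season indicators between the two compared periods (3 df). Take season from the scheduled analysis windows, which depend only on randomization date and sequence. Actual period dates can depend on TF and exacerbation (VI.D, X.D), so use them only as a supplementary check.

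Scheduled windows lose some power when periods move. If 10% end early and 10% are extended (assumed), detection at 1 logit is 87%, against 93% with actual dates. At 20% each it is 80% against 92%. Enrollment season stays at about 5%.

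No change is asked for in the season term of the mixed or hazard models, where no seasonal check is declared. The cost is SAP wording only, because phenotype, sequence and randomization date are already held.
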